## 8.7 Study size

No sample size has been calculated for this disease epidemiology descriptive study, as our primary focus is to examine incidence of ILD, irrespective of the sample size. Based on a preliminary feasibility assessment, the expected number of record counts for ILD in the databases included in this study ranged from 3,900 (CDW/Bordeaux) to 8,800 (IQVIA DA Germany).

## 8.8 Analysis

In principle the type of analysis by study type is fixed as can be observed from [Table 8](#).

	D2.2.3 - Study Protocol for P3-C1-005	
	Author(s): [name] [name]	Version: V2.1
	Dissemination level: Public	

Table 8. Description of Study Types and Type of analysis.

STUDY TYPE	STUDY CLASSIFICATION	TYPE OF ANALYSIS
Population-level descriptive epidemiology	Off-the-shelf (C1)	- Incidence rates of ILD and ILD-subtypes
Patient-level characterisation	Off-the-shelf (C1)	- Patient-level characteristics - Median survival of patients diagnosed with ILD and ILD-subtypes

### 8.8.1 Federated Network Analyses

Analyses will be conducted separately for each database. Before study initiation, test runs of the analytics are performed on a subset of the data sources or on a simulated set of patients and quality control checks are performed. Once all the tests are passed, the final package is released in the version-controlled Study Repository for execution against all the participating data sources.

The data partners locally execute the analytics against the OMOP-CDM in RStudio and review and approve the by default aggregated results before returning them to the Coordination Centre. Sometimes multiple execution iterations are performed, and additional fine tuning of the code base is needed. A service desk will be available during the study execution for support.

The study results of all data sources are checked after which they are made available to the team in the Digital Research Environment (DRE) and the Study Dissemination Phase can start. All results are locked and timestamped for reproducibility and transparency.

### 8.8.2 Patient privacy protection

Cell suppression will be applied as required by databases to protect people's privacy. Cell counts <5 will be masked.

### 8.8.3 Statistical model specification and assumptions of the analytical approach considered

*Objective 1. Incidence of Diagnosed ILD and Common Subtypes:* Calculation of population-based incidence rates is part of our pipelines for population-level descriptive epidemiology. This analysis will be performed using the *IncidencePrevalence* R package and will provide overall incidence rates, stratified by age, sex, and calendar year. (Ed 2024) Additionally, it can be repeated for prespecified ILD subtypes (alveolitis/pneumonitis (excluding aspiration and infectious pneumonitis), lung fibrosis and drug induced ILD). To ensure the reliable estimation of incidence rate of ILD using an appropriate denominator population, this objective will be investigated within the primary care databases: BIFAP, CPRD GOLD, and IQVIA DA Germany.

	D2.2.3 - Study Protocol for P3-C1-005	
	Author(s): [name] [name]	Version: V2.1
	Dissemination level: Public	

*Objective 2. Characterization of Patients Diagnosed with ILD:* Description of patient characteristics is part of our pipelines for patient-level characterisation. Characterization of patient demographics, comorbidities, risk factors, and treatments before diagnosis, as well as characterizing common ILD subtypes at diagnosis, will be conducted using the *CohortCharacteristics* and *CohortDiagnostics* R packages. (Marti 2024) This objective can be explored in all participating databases.

*Objective 3. Survival Rates in Patients Diagnosed with ILD:* Estimation of survival rates is part of our pipelines for patient-level characterisation. *CohortSurvival* R package can estimate survival rates stratified by age, sex, and year. Analysis can be repeated for the prespecified ILD subtypes, subject to sufficient data availability. (Ed 2024) This objective will be investigated in databases with complete mortality data such as BIFAP, CPRD GOLD and CDWBordeaux.

#### 8.8.4 Methods to derive parameters of interest

All methods to derive parameters are predefined using the R packages specified in 8.8.3.

#### 8.8.5 Methods planned to obtain point estimates with confidence intervals of measure of occurrence

##### ***Disease epidemiology study***

##### **Incidence calculations of ILD**

Annual incidence rates of ILD will be calculated as the number of newly diagnosed ILD per 100,000 person-years of the population at risk of the condition during the period for each calendar year. Those study participants who enter the denominator population will then contribute time at risk up to their first diagnosis during the study period. If they do not have the condition of interest, they will contribute time at risk up as described above. Time-at-risk of subjects who die will be censored at the time of death. Similarly, time at risk of subjects who are lost to follow-up will be censored at the time of loss to follow-up (last contact). Subjects with data until the end of the study period without a record of the condition will be administratively censored at the end of the study period. Incidence rates will be given together with 95% Poisson confidence intervals.

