**Table 1. Primary and secondary research questions and objective.**

#### **A. Primary research question and objective.**

Objective:	
Objective 1: To measure the incidence of diagnosed ILD in four European countries, overall and stratified by age, sex and calendar time. This analysis will be repeated for the following ILD subtypes: alveolitis/pneumonitis (excluding aspiration and infectious pneumonitis), lung fibrosis and drug induced ILD).
 
Objective 2: To describe the characteristics of patients diagnosed with ILD in four European countries in terms of demographics (age and sex), comorbidities, and medications used in the one year prior to diagnosis. This analysis will be repeated for the following ILD subtypes: alveolitis/pneumonitis (excluding aspiration and infectious pneumonitis), lung fibrosis and drug induced ILD).
 
Objective 3: To measure survival rates in patients diagnosed with ILD in four European countries overall and stratified by age, sex and calendar time. This analysis will be repeated for the following ILD subtypes: alveolitis/pneumonitis (excluding aspiration and infectious pneumonitis), lung fibrosis and drug induced ILD).

Hypothesis:	Not applicable
Population (mention key inclusion-exclusion criteria):	All patients should be present in the databases with at least 365 days of prior history (except for CDWBordeaux) and be newly diagnosed with ILD (i.e. no prior diagnosis of ILD).
Exposure:	None

	D2.2.3 - Study Protocol for P3-C1-005	
	Author(s): [name] [name]	Version: V2.1
	Dissemination level: Public	

Comparator:	None
Outcome:	Overall survival (objective 3)
Time (when follow up begins and ends):	Follow-up starts after study start date (1st January 2010) or on the date where there is 1 year of prior history. (one year of history not needed for CDWBordeaux) whatever comes last. For objective 2 and 3, the follow-up starts upon the first diagnosis of ILD. The End of follow-up will be defined as the earliest of loss to follow-up, end of data availability, death, or end of study period (31st of December 2022), whatever comes first.
Setting:	Primary care data (CPRD GOLD, BIFAP, IQVIA DA Germany) and secondary care data (CDW Bordeaux).

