#### IQVIA Disease Analyser (DA) Germany, Germany

IQVIA Disease Analyzer (DA) Germany is a database of de-identified electronic medical records from specialised and general primary practices (GP) in Germany since 1992. This dataset encompasses approximately 3% of all outpatient practices within Germany, ensuring a substantial representation of the national healthcare landscape. (Rathmann, Bongaerts et al. 2018, Zappacosta, Cascarano et al. 2022) The sampling methods used for practice selection, taking into account physician's demographics, specialty focus, community size category and federal state location, was instrumental in constructing a database that accurately mirrors the diverse spectrum of healthcare providers in the country. (Rathmann, Bongaerts et al. 2018) Consequently, data within IQVIA DA Germany database has been demonstrated to be representative of general and specialised practices throughout Germany.

The database contains demographics records, basic medical data, disease diagnosis according to International Classification of Diseases, 10th revision (ICD-10), and prescription records. (Zappacosta, Cascarano et al. 2022) While the database partly records information on deaths and procedures, it currently does not support linkage with external data sources and therefore information on mortality is incomplete. Routine updates are conducted at regular intervals. The quality of data is assessed based on several criteria including completeness of information and correctness (e.g. linkage between diagnosis and prescriptions).

IQVIA DA Germany is suitable for pharmacoepidemiologic and pharmaco-economic studies as previously demonstrated. (Tanislav, Rosenbauer et al. 2022, Zappacosta, Cascarano et al. 2022, Ly, Flach et al. 2023).

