## 8.4 Follow-up

**Table 4.** Operational Definition of Time 0 (index date) and other primary time anchors.

[figure not shown]
Study population name(s)	Time Anchor Description (e.g. time 0)	Number of entries	Type of entry	Washout window	Care Setting 	Code Type 	Incident with respect to...
All individuals from the respective databases with at least 1 year of valid database history (not for CDWBordeaux).	Study entry date	Single entry	Incident	Anytime prior to study entry date	IP, OP, OT	SNOMED	Diagnosis of ILD
Patients newly diagnosed with ILD	Date of incident ILD	Single entry	Incident	Anytime prior to ILD	IP, OP, OT	SNOMED	Diagnosis of ILD

 IP = inpatient, OP = outpatient, ED = emergency department, OT = other, n/a = not applicable

	D2.2.3 - Study Protocol for P3-C1-005	
	Author(s): [name] [name]	Version: V2.1
	Dissemination level: Public	

To calculate incidence rates, it is important to have an appropriate denominator population and their contributed observation time. Study participants in the denominator population will begin contributing person time on the respective date of the latest of the following: 1) study start date (1st January 2010), 2) date at which they have 1 year of prior history. Participants will stop contributing person time at the earliest date of the following: 1) end of available data in each of the data sources (date of last data extraction), 2) death, 3) study end date (31st December 2022) or 4) date at which the observation period of the specific person ends (individual leaving practice or being diagnosed with ILD whatever comes first)

An example of entry and exit into the denominator population is shown in **Figure 1**. In this example, person ID 1 has already sufficient prior history before the study start date and observation period ends after the study end date, so will contribute during the complete study period. Person ID 2 and 4 enter the study only when they have sufficient prior history. Person ID 3 leaves when exiting the database (the end of observation period). Lastly, person ID 5 has two observation periods in the database. The first period contributes time from study start until end of observation period, the second starts contributing time again once sufficient prior history is reached and exits at study end date.

**Figure 1.** Included observation time for the denominator population.

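### Section 8.8.5 censors people lost to follow-up at last contact, while 8.4 counts them until they leave the practice; taken literally, 8.8.5 would bias ILD incidence upward in CPRD GOLD and BIFAP

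*Protocol*

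**What the plan says.** Three places in the protocol say when time at risk ends for the incidence analysis.

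- Section 8.4 (Follow-up) lists the stop dates for the denominator. The last is the "date at which the observation period of the specific person ends (individual leaving practice or being diagnosed with ILD whatever comes first").
- Section 8.8.5 (Incidence calculations of ILD) first points back to that rule: "If they do not have the condition of interest, they will contribute time at risk up as described above". It then adds: "Similarly, time at risk of subjects who are lost to follow-up will be censored at the time of loss to follow-up (last contact").
- Table 1 in section 7 ends follow-up at the "earliest of loss to follow-up, end of data availability, death, or end of study period (31st of December 2022), whatever comes first", without defining loss to follow-up.

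Section 8.8.3 names the databases for this objective: "this objective will be investigated within the primary care databases: BIFAP, CPRD GOLD, and IQVIA DA Germany". Section 8.2 mentions practice registration and transfer-out dates for CPRD GOLD, and says that 98.9% of the Spanish population is registered with a primary care physician. For IQVIA DA Germany it mentions neither a patient list nor a leaving date, and says that "it currently does not support linkage with external data sources and therefore information on mortality is incomplete".

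**The concern.** Leaving the practice and last contact are different events. A registered person may go a year without a visit and then transfer out. Under 8.4 that year counts as time at risk; under 8.8.5 it does not. The protocol does not leave the matter open for a later document: it writes the rule twice, differently, for the same denominator.

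The choice is not neutral where people are registered. Time after the last contact contains no recorded diagnosis by construction, so cutting it shrinks the denominator and leaves the numerator unchanged. Section 8.7 calls incidence the primary focus. Rates will be shown for each database separately, and a reader will set them side by side. If each data partner or programmer settles the ambiguity in their own way, part of any difference between countries would come from the censoring rule.

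**Working it through.** The protocol states no incidence rate, person-time or precision that depends on the censoring rule, so there is no figure of its own to reproduce. The check covers direction first, then a range under stated assumptions.

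**Direction.** Rate = cases / person-years. Let f be the share of true person-time that falls after the last contact among people later lost. Under the last-contact rule:

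- cases are unchanged, because a diagnosis is a contact and cannot come after the last one;
- person-years become (1 − f) × true person-years;
- rate ratio (last contact / leaving practice) = 1 / (1 − f), which exceeds 1 whenever f > 0.

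This applies where leaving is observable: CPRD GOLD (transfer-out date, section 8.2), and BIFAP on the reasonable assumption that its registered population has recorded exits.

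**Illustrative size.** All inputs are assumptions. Let p be the share of people lost to follow-up (0.30 to 0.60), g the gap from last contact to leaving (0.25 to 1 year), and T the mean time at risk (5 years). Then f = p × g / T.

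- Low end: f = 0.30 × 0.25 / 5 = 0.015; ratio = 1 / 0.985 = 1.015, a rise of 1.5%.
- High end: f = 0.60 × 1 / 5 = 0.12; ratio = 1 / 0.88 = 1.136, a rise of about 14%.

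**A second set of assumptions.** Suppose contacts occur at random at L per year over T registered years, and every non-case is cut at last contact. Then f = (1 − exp(−L × T)) / (L × T).

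| T (years) | L = 4 | L = 2 | L = 1 | L = 0.5 |
|---|---|---|---|---|
| 5 | 1.05 | 1.11 | 1.25 | 1.58 |
| 13 | 1.02 | 1.04 | 1.08 | 1.18 |

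This version is harsher than the text of 8.8.5, which applies last contact only to people lost and censors those with data to the end of the study administratively. It confirms the direction and shows how strongly the size depends on inputs that the protocol does not give.

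**Against sampling error.** If the feasibility counts in Table 3 were the incident cases (an assumption), the relative half-width of a 95% Poisson interval is 1.96 / √n:

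- CPRD GOLD: 1.96 / √6,900 = 2.4%;
- BIFAP: 1.96 / √7,900 = 2.2%.

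Most of the 1.5 to 14% range is wider than these overall intervals, and the intervals would not reveal the bias. For an average single year (n / 13) the half-widths are about 8.5% and 8.0%, so there the bias could be smaller or larger than the sampling error.

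**The case against.** The best reply is that there is only one rule. Section 8.8.5 refers back to 8.4. The operative term in 8.4 is the end of the observation period, and the example beneath it says that a person leaves on exiting the database. On this reading, last contact is a loose gloss, section 8.8.4 leaves derivation to the named R packages, and those would use each database's observation period whatever the prose says. This may well be what is intended. But the text does not say so, and last contact is not another name for leaving a practice. The reply removes the bias only if the gloss is ignored, which is a reason to delete it.

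It is also fair that the bias is limited by the administrative censoring of people with data to the end of the study, and that every input to the size is assumed. Both points stand.

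A reader might go further and infer that either rule biases incidence in all three databases, in opposite directions. The documents do not support that. Leaving the practice is a suitable end date where registration is recorded, so 8.4 is not at fault for CPRD GOLD, nor for BIFAP if its exits are recorded. A downward bias in IQVIA DA Germany would require observation periods there to run on after unrecorded departures or deaths. The protocol says only that mortality is incomplete; it does not say how observation periods are built. If they already end at last activity, the inflation does not arise. Nor would prescribing last contact for IQVIA be a clear remedy, since it could bring in the same upward mechanism described above.

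One might also fault the stop date at last data extraction, because every lock date in Table 3 falls after 31 December 2022. A stop date that never binds in a list of earliest dates does no harm and is not an error.

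**Conclusion.** The inconsistency is real. Sections 8.4 and 8.8.5 give different end dates for the same time at risk, and Table 1 defines neither. If 8.8.5 is followed literally in CPRD GOLD and BIFAP, incidence is biased upward. That direction follows from the definition of the rate, given that people are registered and their exits recorded (stated for CPRD GOLD, assumed for BIFAP).

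The size cannot be derived from the document. It is about 1.5 to 14% under the assumed inputs (30 to 60% lost, a gap of 0.25 to 1 year, 5 years at risk), and other plausible assumptions move it widely.

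For IQVIA DA Germany the documents show a gap in description, not a bias. Section 11 draws the consequence of incomplete deaths for survival but does not mention the incidence denominator. A downward effect there, chiefly at older ages, remains conditional on how observation periods end. The point deserves correction because incidence is the primary focus and the change is nearly free.

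**What to change.** 1. In section 8.8.5, delete the bracketed reference to last contact.
2. In Table 1 and section 8.8.5, define loss to follow-up as the end of the observation period in section 8.4.
3. In section 8.4, state what this date is for CPRD GOLD and BIFAP: deregistration or transfer-out, or the last data supply if that is earlier.
4. For IQVIA DA Germany, ask the data partner which date ends the observation period, and state it in 8.4.
5. In section 11, add that incomplete death recording in IQVIA DA Germany may also affect the incidence denominator, chiefly at older ages, if observation periods can run past unrecorded deaths.

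The cost is a few sentences in Table 1 and sections 8.4, 8.8.5 and 11, plus one query to each data partner on how observation periods were built. No extra data are needed.

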##### Output

- Table 1. Number of participants, total number of incident cases and total time at risk in each data source during the study period. Number of participants per pre-specified strata will be included where necessary/applicable.
- Figure 1. Incidence rate/s of disease over calendar time (year) overall
- Figure 2. Incidence rate/s of disease over calendar (year) stratified by sex and age
- Table 2. Numbers reported in figures 1 and 2

##### ***Patient-level characterisation study***

##### **Patient-level characteristics on index date**

For each concept extracted at index date, the number of individuals (N, %) with a record of the drug and condition of interest within the pre-specified time windows will be provided. For all analyses n and % will be reported. A minimum cell counts of 5 will be used when reporting results, with any

	D2.2.3 - Study Protocol for P3-C1-005	
	Author(s): [name] [name]	Version: V2.1
	Dissemination level: Public	

smaller counts reported as “<5”. All analyses will be reported by country/database, overall and stratified by age group, sex when possible (minimum cell count reached).

### **Overall survival on index date**

The number and % of patients with all-cause mortality will be reported from time of ILD diagnosis to the date of death. Survival estimates for each subject following diagnosis of ILD and each ILD-subtype will be calculated. These will be presented as median survival and 95% confidence intervals overall, per ILD-subtype and per strata (age category at first diagnosis and sex). Individuals who are lost to follow-up will be censored at the time of loss of follow-up.

### **Output**

- Table 1. Baseline characteristics (prespecified comorbidities and drugs) of newly diagnosed ILD patients.
- Table 2. Number and % of individuals who died following ILD diagnosis.
- Figure 1. Kaplan-Meier or Cumulative Incidence Function plots of the probability of a pre-specified outcome (overall survival) following index diagnosis of the condition of interest.

### **8.8.6 Methods to deal with missing data**

For the disease epidemiology studies we assume that the absence of a diagnosis record means that the person did not receive the diagnosis.

## **8.9 Evidence synthesis**

Results from analyses described in section 8.8 **Data analysis** will be presented separately for each database and no meta-analysis of results will be conducted.

# **9. DATA MANAGEMENT**

## **9.1 Data management**

All databases are mapped to the OMOP common data model. This enables the use of standardised analytics and tools across the network since the structure of the data and the terminology system is harmonised. The OMOP CDM is developed and maintained by the Observational Health Data Sciences and Informatics (OHDSI) initiative and is described in detail on the wiki page of the CDM: <https://ohdsi.github.io/CommonDataModel> and in The Book of OHDSI: <http://book.ohdsi.org>.

The analytic code for this study will be written in R. Each data partner will execute the study code against their database containing patient-level data and will then return the results set which will only contain aggregated data. The results from each of the contributing data sites will then be combined in tables and figures for the study report.

## **9.2 Data storage and protection**

For this study, participants from various EU member states will process personal data from patients which is collected in national/regional electronic health record databases. Due to the sensitive nature of this

	D2.2.3 - Study Protocol for P3-C1-005	
	Author(s): [name] [name]	Version: V2.1
	Dissemination level: Public	

personal medical data, it is important to be fully aware of ethical and regulatory aspects and to strive to take all reasonable measures to ensure compliance with ethical and regulatory issues on privacy.

All databases used in this study are already used for pharmaco-epidemiological research and have a well-developed mechanism to ensure that European and local regulations dealing with ethical use of the data and adequate privacy control are adhered to. In agreement with these regulations, rather than combining person level data and performing only a central analysis, local analyses will be run, which generate non-identifiable aggregate summary results.

The output files are stored in the DARWIN Digital Research Environment. These output files do not contain any data that allow identification of subjects included in the study. The DRE implements further security measures to ensure a high level of stored data protection to comply with the local implementation of the General Data Protection Regulation (GDPR) (EU) 679/20161 in the various member states.

